### **Data Sources for Endpoints**

Migraine days, acute migraine-specific medication days, acute migraine medication days, and headache days are derived from eDiary data from the external source YPrime. Acute migraine-specific medications are triptans and ergotamine. Acute migraine medications are triptans, ergotamine, and other protocol-allowed medications to treat headache or aura taken on migraine days.

AEs are determined from AE case report forms (CRFs).

Grade 3 to 4 laboratory test abnormalities are determined from laboratory test values graded using standardized criteria. Laboratory test results are from an external central laboratory and local laboratory test CRFs.

C-SSRS parameters, MSQ scores, and MIDAS scores are derived from their respective CRFs.

# 3.2.1 Primary Objective Estimand

The estimand corresponding to the primary endpoint is shown in Table 1.

Table 1 Primary Objective Estimands

Objective	Mean reduction from the OP in the number of migraine days per month over the entire DBT Phase
Efficacy Endpoint	Mean change from OP in the number of migraine days per month over the entire DBT Phase (Weeks 1 to 12)
Summary	Mean change from OP by treatment group using descriptive statistics and linear mixed effects model with repeated measures, and difference between treatment groups from model for the migraine analysis set
Intercurrent Events	Study drug discontinuation: hypothetical strategy
	Non-study prophylactic migraine medication use: treatment policy strategy
	Nonstudy acute migraine-specific medication use: composite strategy
	Use of nonstudy other medication to treat headache (migraine or nonmigraine) or aura: treatment policy strategy

# 3.2.2 Secondary Objective Estimands

The estimands corresponding to the secondary objectives are shown in Table 2.

Table 2 Secondary Objective Estimands

Objective 1	Proportion of subjects with ≥ 50% reduction from the OP in the number of moderate or severe migraine days per month over the entire DBT Phase
Efficacy Endpoint	Proportion of subjects with $\geq 50\%$ reduction from OP in number of moderate or severe migraine days per month over the entire DBT Phase (Weeks 1 to 12)
Summary	Percentages by treatment group, and difference in percentages between treatment groups using Mantel-Haenszel risk estimation with stratification by randomization stratum for the migraine analysis set
Intercurrent Events	Study drug discontinuation: composite strategy
	Non-study prophylactic migraine medication use: treatment policy strategy
	Nonstudy acute migraine-specific medication use: composite strategy
	Use of nonstudy other medication to treat headache (migraine or nonmigraine) or aura: treatment policy strategy
Objective 2	Mean reduction from the OP in the number of migraine days per month in the last 4 weeks of the DBT Phase

Efficacy Endpoint	Mean change from OP in the mean number of migraine days per month in the last 4 weeks (Weeks 9 to 12) of the DBT Phase
Summary	Mean change from OP by treatment group using descriptive statistics and linear mixed effects model with repeated measures, and difference between treatment groups from model for the migraine analysis set
Intercurrent Events	Study drug discontinuation: hypothetical strategy
	Non-study prophylactic migraine medication use: treatment policy strategy
	Nonstudy acute migraine-specific medication use: composite strategy
	Use of nonstudy other medication to treat headache (migraine or nonmigraine) or aura: treatment policy strategy
Objective 3	Mean reduction from the OP in the number of migraine days per month in the first 4 weeks of the DBT Phase
Efficacy Endpoint	Mean change from OP in the number of migraine days per month in the first 4 weeks (Weeks 1 to 4) of the DBT Phase
Summary	Mean change from OP by treatment group using descriptive statistics and linear mixed effects model with repeated measures, and difference between treatment groups from model for the migraine analysis set
Intercurrent Events	Study drug discontinuation: hypothetical strategy
	Non-study prophylactic migraine medication use: treatment policy strategy
	Nonstudy acute migraine-specific medication use: composite strategy
	Use of nonstudy other medication to treat headache (migraine or nonmigraine) or aura: treatment policy strategy
Objective 4	Mean number of acute migraine-specific medication days per month over the entire DBT Phase
Efficacy Endpoint	Mean number of acute-migraine-specific days per month over the entire DBT Phase (Weeks 1 to 12)
Summary	Mean value by treatment group using descriptive statistics and linear mixed effects model with repeated measures, and difference between treatment groups from model for the migraine analysis set
Intercurrent Events	Study drug discontinuation: hypothetical strategy
	Non-study prophylactic migraine medication use: treatment policy strategy
	Nonstudy acute migraine-specific medication use: not applicable
	Use of nonstudy other medication to treat headache (migraine or nonmigraine) or aura: treatment policy strategy
Objective 5	Mean change from baseline in the MSQ restrictive role function domain score at Week 12 of the DBT Phase
Outcomes Research Endpoint	Mean change from baseline in the MSQ restrictive role function domain score at Week 12 of the DBT Phase
Summary	Mean change from baseline by treatment group using descriptive statistics and linear regression model, and difference between treatment groups from model for the DBT efficacy analysis set
	criticacy analysis set
Intercurrent Events	Study drug discontinuation: treatment policy strategy

	Nonstudy acute migraine-specific medication use: treatment policy strategy
	Use of nonstudy other medication to treat headache (migraine or nonmigraine) or aura: treatment policy strategy
Objective 6	Mean change from baseline in the MIDAS total score at Week 12 of the DBT Phase
Outcomes Research Endpoint	Mean change from baseline in the MIDAS total score at Week 12 of the DBT Phase
Summary	Mean change from baseline by treatment group using descriptive statistics and linear regression model and difference between treatment groups from model for the DBT efficacy analysis set
Intercurrent Events	Study drug discontinuation: treatment policy strategy
	Non-study prophylactic migraine medication use: treatment policy strategy
	Nonstudy acute migraine-specific medication use: treatment policy strategy
	Use of nonstudy other medication to treat headache (migraine or nonmigraine) or aura: treatment policy strategy
Objective 7	Safety and tolerability of zavegepant during the DBT and OLE Phases
Safety Endpoint	Number and percentage of subjects with AEs by intensity, serious adverse events (SAEs), AEs leading to study drug discontinuation, and grade 3 to 4 laboratory test abnormalities on treatment
Summary	Frequency by treatment group for the DBT and OL zavegepant safety analysis sets
Intercurrent Events	Study drug discontinuation: while-on-treatment strategy
	Non-study prophylactic migraine medication use: treatment policy strategy
	Nonstudy acute migraine-specific medication use: treatment policy strategy
	Use of nonstudy other medication to treat headache (migraine or nonmigraine) or aura: treatment policy strategy
Objective 8	Frequency of ALT or AST > 3x upper limit of normal (ULN) concurrent with TBL > 2x ULN in subjects treated with zavegepant during the DBT and OLE Phases
Safety Endpoint	Number and percentage of subjects with AST or ALT elevations $> 3x$ ULN concurrent (i.e., on the same laboratory collection date) with TBL $> 2x$ ULN on treatment
Summary	Frequency by treatment group for the DBT and OL zavegepant safety analysis sets with LFT data
Intercurrent Events	Study drug discontinuation: while-on-treatment strategy
	Non-study prophylactic migraine medication use: treatment policy strategy Nonstudy acute migraine-specific medication use: treatment policy strategy
	Use of nonstudy other medication to treat headache (migraine or nonmigraine) or aura: treatment policy strategy
Objective 9	Frequencies of hepatic-related AEs and hepatic-related AEs leading to study drug discontinuation in subjects treated with zavegepant during the DBT and OLE Phases
Safety Endpoint	Number and percentage of subjects with hepatic-related AEs and hepatic-related AEs leading to study drug discontinuation on treatment
Summary	Frequency by treatment group for the DBT and OL zavegepant safety analysis sets

Intercurrent Events Study drug discontinuation: while-on-treatment strategy

Non-study prophylactic migraine medication use: treatment policy strategy Nonstudy acute migraine-specific medication use: treatment policy strategy

Use of nonstudy other medication to treat headache (migraine or nonmigraine) or aura:

treatment policy strategy

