3.2 Secondary Endpoint(s)

- 1. Proportion of subjects with $\geq 50\%$ reduction from the Observation Phase in the number of moderate to severe migraine days per month over the entire DBT Phase (Weeks 1 to 12).
- 2. Mean change from the Observation Phase in the number of migraine days per month in the last 4 weeks (Weeks 9 to 12) of the DBT Phase.
- 3. Mean change from the Observation Phase in the number of migraine days per month in the first 4 weeks (Weeks 1 to 4) of the DBT Phase.
- 4. Mean number of acute migraine-specific medication days per month over the entire DBT Phase (Weeks 1 to 12). Acute migraine-specific medications are triptans and ergotamine (see Section 3.3).
- 5. Mean change from baseline in the MSQ restrictive role function domain score at Week 12 of the DBT Phase.
- 6. Mean change from baseline in the MIDAS total score at Week 12 of the DBT Phase.
- 7. Number and percentage of subjects with AEs by intensity, SAEs, AEs leading to study drug discontinuation, and grade 3 to 4 laboratory test abnormalities during the DBT and OLE Phases.
- 8. Number and percentage of subjects with AST or ALT elevations > 3x ULN concurrent (i.e., on the same laboratory collection date) with total bilirubin > 2x ULN during the DBT and OLE Phases.
- 9. Number and percentage of subjects with hepatic-related AEs by intensity, and hepatic-related AEs leading to study drug discontinuation during the DBT and OLE Phases.

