6.2.4.1 Safety Laboratory Testing

Blood and urine samples will be obtained as outlined in Table 1 and Table 2 for clinical laboratory evaluations. A central laboratory vendor will be utilized for this study and a laboratory manual will be provided to each site. If possible, subjects should be fasting for a minimum of 8 hours before laboratory tests. However, if a subject is not fasting at a given visit, the blood draw should still be performed, and the non-fasting status should be documented

1. Clinical safety labs:

Hematology: Hemoglobin, hematocrit, red blood cell count, white blood cell count with differential, and platelets;

Chemistry: Sodium, potassium, chloride, bicarbonate, calcium; glucose, BUN (urea), serum creatinine, uric acid, LDH, total protein, albumin.

eGFR estimated using the MDRD formula (calculated at central lab).

- 2. **LFTs**: AST, ALT, Alkaline Phosphatase and Bilirubin (Total, Direct, Indirect), CK (fractionation will be ordered if CK result is > 5.0x ULN).
- 3. HbA1c
- 4. **Lipid panel:** Cholesterol, LDL, HDL, triglycerides.
- 5. **Urinalysis:** pH, specific gravity, ketones, nitrites, urobilinogen, leukocyte esterase, protein, glucose, and blood. If blood, protein or leukocytes are positive, reflex to microscopic examination.
- 6. **Urine Drug Screen:** For drugs of abuse.
- 7. **FSH:** At screening in female subjects to confirm postmenopausal status, if applicable.

Additional tests may be required to evaluate laboratory abnormalities and/or adverse events; please refer to the Laboratory Manual.

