8.4 Potential Drug Induced Liver Injury (DILI)

Wherever possible, timely confirmation of the initial liver-related laboratory abnormalities should occur prior to the reporting of a potential DILI event. All occurrences of potential DILIs, meeting the defined criteria, must be reported as SAEs as per Section 8.1.2.

Potential drug induced liver injury is defined as:

1. ALT or AST elevation > 3x ULN

AND

2. Total bilirubin > 2x ULN, without initial findings of cholestasis (elevated serum alkaline phosphatase)

AND

3. No other immediately apparent possible causes of ALT or AST elevation and hyperbilirubinemia, including but not limited to, viral hepatitis, pre-existing chronic or acute liver disease, or the administration of other drug(s) known to be hepatotoxic.

If any potential DILI is identified and meets the criteria above, the Biohaven Medical Monitor (or designee) should immediately be contacted for further instruction and whether the subject must discontinue from the trial and appropriate follow-up requirements.

8.5 **Adverse Events of Special Interest**

Not applicable.

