9.3.2 Safety Analyses

Deaths will be listed regardless of onset for the enrolled analysis set.

The frequencies of safety endpoints will be assessed descriptively as the number and percentage of subjects with events/findings separately for the 3 safety analysis sets.

The frequencies of the following safety endpoints will be tabulated on treatment: AEs by intensity (mild, moderate, severe, total); AEs by relationship to study drug (related, possibly related, unlikely related, not related); SAEs; AEs leading to study drug discontinuation; hepatic-related AEs by intensity; hepatic-related AEs leading to study drug discontinuation; clinically significant laboratory test abnormalities; and LFT elevations based on fold changes above ULN, including ALT or AST > 3x ULN concurrent (on the same laboratory test collection date) with total bilirubin > 2x ULN.

The investigators will determine the intensity of AEs and the relationship of AEs to study drug. The investigators' terms will be coded using the latest version of the Medical Dictionary for Regulatory Activities (MedDRA) available at the start of the study. AEs will be tabulated by system organ class and preferred term. In tables by intensity, if a subject has an AE with different intensities over time, then only the greatest intensity will be reported. In tables by relationship to study drug, if a subject has an AE with different relationships over time, then the highest degree of relatedness to study drug will be reported.

Clinically significant laboratory test abnormalities will be identified as grade 3 to 4 laboratory test results graded according to numeric laboratory test criteria in Common Terminology Criteria for Adverse Events (CTCAE) Version 5.0 (2017), if available. Otherwise, if CTCAE grades are not available, then results will be graded according to numeric laboratory test criteria in Division of AIDS (DAIDS) Table for Grading the Severity of Adult and Pediatric Adverse Events Corrected Version 2.1 (2017). If a subject has a laboratory test abnormality with different toxicity grades over time, then only the highest toxicity grade will be reported.

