#### **Intercurrent Events**

Intercurrent events are those that occur after treatment initiation and either preclude observation of the endpoint or affect its interpretation.

Study drug discontinuation before the time point of interest defining the endpoint is considered an intercurrent event.

• For efficacy objectives assessed with a continuous endpoint during the DBT Phase, study drug discontinuation is handled with a "hypothetical strategy," i.e., the hypothetical scenario is that had subjects not discontinued DB study drug, their efficacy would have been similar to the efficacy of subjects from the same treatment group and randomization stratum who did not discontinue DB study drug. All observed values of the endpoint of interest are excluded after DB study drug discontinuation (see Section 7.2), and statistical methods are used to estimate the treatment effect that would have been seen had the intercurrent event not occurred.

- For efficacy objectives assessed with a binary endpoint during the DBT Phase, DB study drug discontinuation is handled with a "composite strategy," i.e., the occurrence of the intercurrent event is integrated as a component of the endpoint. All observed values of the endpoint of interest are excluded after DB study drug discontinuation (see Section 7.2), and subjects with missing data are considered failures.
- For safety objectives, study drug discontinuation is handled with a "while-on-treatment strategy". All observed values of the endpoint of interest are used on or before study drug discontinuation + 7 days (see Section 7.2 and the Core SAP).
- For outcomes research and other objectives, study drug discontinuation is handled with a "treatment policy strategy", i.e., the occurrence of the intercurrent event is considered irrelevant, such that all observed values of the endpoint of interest are used regardless of study drug discontinuation.

Non-study prophylactic migraine medication use before the time point of interest defining the endpoint is also considered an intercurrent event. For all objectives, this intercurrent event is handled with a treatment policy strategy, such that all observed values of the endpoint of interest are used.

Nonstudy acute migraine-specific medication use before the time point of interest defining the endpoint is also considered an intercurrent event, except for efficacy objectives based on acute migraine-specific medication days or acute migraine medication days.

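### Secondary endpoint 8 counts only same-date transaminase and bilirubin elevations, so a non-overlapping pair that meets the protocol 8.4 laboratory thresholds adds nothing to it, and no described output counts such pairs by treatment group

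*SAP*

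**What the plan says.** **Endpoint 8.** The protocol and SAP agree. Protocol 3.2, item 8, requires the transaminase elevation to be "concurrent (i.e., on the same laboratory collection date) with total bilirubin > 2x ULN during the DBT and OLE Phases". Protocol 9.3.2 repeats the rule: "ALT or AST > 3x ULN concurrent (on the same laboratory test collection date) with total bilirubin > 2x ULN". SAP 3.2.2, Table 2, Objective 8 has AST or ALT above 3x "ULN concurrent (i.e., on the same laboratory collection date) with TBL" above 2x ULN, on treatment, among subjects with LFT data.

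**Potential DILI.** Protocol 8.4 has three joint conditions. The first is "ALT or AST elevation > 3x ULN". The second is "Total bilirubin > 2x ULN, without initial findings of cholestasis". The third is that no other cause is immediately apparent. It sets no condition on dates. It asks for confirmation of the initial abnormality where possible, and states: "All occurrences of potential DILIs, meeting the defined criteria, must be reported as SAEs".

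**Window.** For safety objectives, SAP 3.2 (Intercurrent Events) says: "All observed values of the endpoint of interest are used on or before study drug discontinuation + 7 days".

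**Panel.** Protocol 6.2.4.1 draws the liver tests as one group: "AST, ALT, Alkaline Phosphatase and Bilirubin (Total, Direct, Indirect), CK".

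**The concern.** The protocol applies two timing rules to one pair of laboratory thresholds, and the tabulated endpoint uses the narrower rule. Liver tests are scheduled weeks apart, so transaminases can fall before bilirubin peaks. The two elevations are then seen on different draws and never together. Such a subject could be reported as a potential DILI serious adverse event while the endpoint 8 table shows no case.

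This matters because two of the three safety secondary objectives are hepatic (items 8 and 9 of Protocol 2.2), and because the linked pair is the liver signal that endpoint 8 is meant to compare between arms. Separate ALT, AST and bilirubin tables cannot show whether the same subject had both elevations.

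**Working it through.** The documents state no figure for this point, so there is none to reproduce. The check compares the rules, applies them to example sequences, and then shows the weight of one case.

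**1. Rules side by side**

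| Condition | Endpoint 8 | Protocol 8.4 |
|---|---|---|
| ALT or AST > 3x ULN | yes | yes |
| TBL > 2x ULN | yes | yes |
| Same collection date | required | not stated |
| No initial cholestasis | not required | required |
| No other apparent cause | not required | required |

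**2. What is missed.** Every same-date pair is also an any-date pair, so endpoint 8 can only equal or fall below a count based on the two laboratory thresholds alone. Because ALT, AST and bilirubin share a panel, each scheduled draw with TBL > 2x ULN also has transaminase values. A subject who meets both thresholds is missed only if ALT and AST are ≤ 3x ULN at every draw where TBL is > 2x ULN.

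**3. Example sequences** (assumed values; ALT and TBL as multiples of ULN)

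| Day 29 | Day 57 | Same-date rule | Any-date rule |
|---|---|---|---|
| 6.0 / 1.0 | 3.5 / 2.4 | counted | counted |
| 6.0 / 1.0 | 2.2 / 2.4 | not counted | counted |

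**4. Spacing.** Protocol Tables 1 and 2 schedule LFTs at Days 15, 29, 57, 86, 99 and 113, then every 28 days to Day 449. The gaps are 14, 28, 29, 13, 14 and then 28 days. With visit windows of ±2 days, a 28-day gap can reach 28 + 2 + 2 = 32 days. Week 8 to Week 12 can reach 29 + 2 + 3 = 34 days. A non-overlapping pair is therefore possible between consecutive scheduled draws.

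**5. End of treatment.** The on-treatment window closes 7 days after the last dose. Follow-up Week 2 is 14 ± 2 days after the last treatment visit, so 12 to 16 days. If the last dose was on or before that visit, the draw falls outside the window. A bilirubin rise first seen there cannot enter endpoint 8 under any date rule. If both elevations fall on that one draw, the follow-up LFT table in SAP 6.4.2.2 can show them. If the transaminase elevation was on treatment and only the bilirubin elevation is in follow-up, neither period contains the pair.

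**6. Weight of one case.** Inputs: n = 480, the planned number randomized per zavegepant group (Protocol 9.1), used as an assumption; confidence level 97.5% (SAP 6.4.2.2), so 0.0125 in each tail. The supplied text does not say that these intervals are exact; Clopper-Pearson is used here.

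- 0/480: upper limit = 1 − 0.0125^(1/480) = 0.91%; interval 0 to 0.91%.
- 1/480 = 0.21%: lower limit = 1 − 0.9875^(1/480) = 0.003%; upper limit = 98.75th percentile of Beta(2, 479) = 1.32%.
- Both doses, n = 960: 0% (0 to 0.46%) against 0.10% (0.001% to 0.66%).

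**The case against.** The strongest reply is that the two rules serve different purposes. Section 8.4 is a reporting rule for investigators and needs judgement about cholestasis and cause; endpoint 8 is a programmable laboratory count. The objective itself says concurrent, and the protocol and SAP define that word alike. This stands: the endpoint is prespecified and is not an error of transcription.

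It also stands that the case is not hidden. If reported, it is in the SAE tables (SAP 6.4.1). ALT, AST and TBL elevations are tabulated singly. SAP 6.4.2 lists all LFT results for any subject with ALT or AST > 3x or TBL > 2x ULN, and SAP 6.4.2.2 plans by-subject plots. In SAP 6.4.6, either elevation on zavegepant identifies the subject for a narrative. None of these outputs counts the linked pair by arm, however, and that narrative trigger does not cover placebo treatment. SAP 6.4.2.2 also names composite LFT tables, whose contents are left to the Core SAP. A row for non-concurrent pairs can be neither confirmed nor excluded.

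A reader might go further and infer any of the following. The documents support none of them:

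- *Every later bilirubin rise is missed.* It is counted on treatment if ALT or AST is still > 3x ULN at that draw.
- *Endpoint 8 can only undercount potential DILI.* That holds against the laboratory thresholds alone. Against the full 8.4 definition the rules differ in both directions, since endpoint 8 also counts same-date cases with cholestasis or another cause.
- *The trial would report no liver case at all.* The zero applies to this one endpoint.
- *The SAP departs from the protocol.* It does not. The difference is within the protocol, between 3.2 and 9.3.2 on one side and 8.4 on the other.

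**Conclusion.** The point holds as a gap in the planned outputs. A subject with non-overlapping elevations can meet the 8.4 laboratory thresholds and add zero to endpoint 8, and nothing described in the supplied text counts such subjects by treatment group. It does not justify replacing the prespecified endpoint.

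The size cannot be derived from the documents, which give no rate for such sequences. The illustration shows only that one case in an assumed 480 would move the estimate from 0% to 0.21% and the upper limit from 0.91% to 1.32%. SAP 1 says the study was terminated early and Table 2 restricts the denominator to subjects with LFT data, so the actual n may differ. The conclusion also depends on what the Core SAP puts in its composite rows. A supplementary row is a cheap improvement.

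**What to change.** Leave the same-date count as endpoint 8. In SAP 6.4.2.2:

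- Add a supplementary row, by DB treatment group, for subjects with TBL > 2x ULN on or after the date of an ALT or AST > 3x ULN, within a stated window. Thirty days is an assumption taken from no document; show 14 and 60 days beside it. The second example in the table of sequences spans 57 − 29 = 28 days, so it enters at 30 and 60 days but not at 14. Scheduled gaps of up to 32 or 34 days can exceed 30, which is a reason to show 60.
- Let the pair span the end of treatment through Follow-up Week 8. State how a pair is assigned when a placebo subject has started open-label zavegepant before it is complete.
- List the cases in the row against the serious adverse events reported under 8.4, and explain each difference (cholestasis, other cause, timing, not reported).
- If the Core SAP already has a non-concurrent row, cite it and extend it across the treatment boundary.

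The cost is a short SAP addition and one derived flag from LFT data already collected. The downside is a possibly slightly less favourable liver count. Requiring bilirubin on or after the transaminase elevation leaves out bilirubin-first pairs, although 8.4 states no order, so the row should carry that limit in a footnote.
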